12. STATISTICAL METHODS

12.1. Statistical populations

Analyses will be based on the Enrolled Set, the Safety Analysis Set, the Intent-to-treat (ITT) Set, the Endometrial Safety Analysis Set, the Per-protocol (PP) Set and the modified Intent-to-treat (mITT) Set. The definitions of the analysis sets, with the exception of the mITT, follow those given in the ICH E9 guideline (CMP/ICH/363/96).

Enrolled Set: All subjects who sign the ICF form the Enrolled Set.

Safety Analysis Set: Randomized subjects who receive at least one dose of randomized study medication form the Safety Set. The Safety Analysis Set will be used for all analyses of safety, tolerability, and background characteristics and all analyses on this set will be based on treatment received.

Endometrial Safety Analysis Set: All randomized subjects who received at least one dose of randomized study medication, had an evaluable biopsy at Baseline and at Month 12 (defined by a Visit window as on or after Day 326) or had a diagnosis of endometrial hyperplasia prior to Month 12.

Intent-to-treat (ITT) Set: The ITT Set consists of all randomized subjects who receive at least one dose of randomized study medication. The ITT Set will be the primary analysis population for the efficacy analyses and all analyses on this set will be based on randomized treatment.

Modified Intent-to-treat (mITT) Set: The mITT Set consists of all randomized subjects in the ITT Set excluding subjects presenting at least one of the following features:

- At least one post baseline E4 concentration level below the lower limit of quantification
- At least one post screening E2 concentration level is superior to 40 pg/mL

Per-protocol (PP) Set: Subjects in the ITT Set who do not have major protocol deviations will form the PP Set. The major protocol deviations will be defined at the time of the evaluability assessment between the database soft lock and hard lock before unblinding. The PP Set will be used for efficacy sensitivity analyses and all analyses on this set will be based on randomized treatment.

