Biopsies obtained during screening and during the conduct of the study, including end-of-study biopsies, will be initially read by one safety pathologist for safety diagnosis only. The Investigator will decide inclusion or discontinuation of the subject from the study based on the initial reading. Screening biopsies will also be read by two other expert pathologists. Biopsy samples collected during the conduct of study and at the end-of-study will be read by three expert pathologists for the final (consensus) diagnosis. These three expert pathologists are independent and belong to different institutions. They are blinded to treatment and to each other's readings.

The investigator will be informed if subsequent readings impact the initial decision. A reading of disordered proliferative endometrium, hyperplasia (simple or complex, with or without atypia) or carcinoma from any of the pathologists providing the safety readings will prompt the exclusion or discontinuation of the subject from the study.

The concurrence of two of the three pathologists who read the biopsy samples for final (consensus) diagnosis will be accepted as the Final Diagnosis. If there is no agreement among the three pathologists, the most severe pathologic diagnosis, i.e., carcinoma > atypical complex hyperplasia > atypical simple hyperplasia > complex hyperplasia > simple hyperplasia > benign endometrium will be used as the final diagnosis. The Final Diagnosis will be used for the analysis of the endometrial safety objective.

Standardized criteria as provided in Blaustein's pathology text (Pathology of the Female Genital Tract 8, see Appendix 16.3) will be used for the characterization of the endometrial tissue. Endometrial polyps will be fully characterized as to the glandular proliferation and atypia (see Appendix 16.3 for additional histologic characteristics of the specimen).

Procedure in case of disordered proliferative endometrium, hyperplasia or worse

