If a biopsy shows disordered proliferative endometrium, hyperplasia or worse, the study drug will be discontinued, and the subject will be withdrawn from the study. The subject will be treated with P4 200 mg once daily for 14 days. If the endometrial event has not resolved, treatment with a progestin will be started according to local practice/guidelines. The subject will be followed up (i.e. collect diagnostic and therapeutic assessment(s)) until resolution, even if after study termination. The diagnostic assessment which proves resolution must be reported to the Sponsor even after study termination. In case of disordered proliferative endometrium, hyperplasia or worse, the event must be reported as an Adverse Event of Special Interest (AESI) (Section 10.6) and the Sponsor will be notified.

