10.4.10. Endometrial Safety Assessment and Stopping Rules

A baseline endometrial biopsy will be obtained for all the non-hysterectomized subjects during the Screening period. An end-of-treatment endometrial biopsy is planned at the EoT Visit (Visit

7 in the Efficacy study part and Visit 6 in the Safety Study part) providing that the subject has been treated with E4 for at least 12 weeks.

Endometrial thickness will be measured at screening, Visit 4, Visit 5, Visit 6 and Visit 7 (EoT) in the Efficacy Study part and at screening, Visit 3, Visit 4, Visit 5 and Visit 6 (EoT) in the Safety Study part and subjects will record daily the vaginal bleeding events. If after the first 4 weeks of treatment, subject presents with a bi-layer endometrial thickness >10 mm as assessed by TVUS and/or presents with persistent and/or recurrent bleeding, confirmed by the investigator, an endometrial biopsy will be performed. If the biopsy shows disordered proliferative endometrium, hyperplasia or worse, the study drug will be discontinued, and the subject will be withdrawn from the study. The subject will be treated with P4 200 mg once daily for 14 days. At approximately 10-14 days after completion of the progestin treatment, a new TVUS will be performed to measure endometrial thickness and a biopsy will be carried out if deemed necessary by the Investigator to demonstrate the resolution. If the endometrial event has not resolved, treatment will be started according to local practice/guidelines. The pathologic diagnoses of DPE, hyperplasia and worse will be reported as AESI and the subject will be followed up until the resolution of the event. Resolution of disordered proliferative endometrium and hyperplasia should be documented by TVUS with endometrial thickness ≤4 mm or an endometrial biopsy repeated no earlier than 10-14 days after oral treatment with P4 200 mg/day for 14 days given after discontinuation of the subject.

Information on the treatment (including surgical treatment) and any additional pathology results will be reported.

Endometrial safety will be monitored during the trial by a DSMB (see Section 10.5).

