12.8. Safety parameters (safety set)

All safety parameters will be summarized using data from the Safety Analysis Set if not indicated otherwise. No formal statistical test will be performed to determine statistical significance between treatment groups. Continuous variables will be summarized using descriptive statistics (N, mean, standard deviation, median, minimum, maximum), categorical variables will be presented in frequency tables using counts and percentages. The frequency of endometrial events will be computed on the evaluable biopsies of the endometrium. The incidence of spotting/bleeding will be analyzed by a 28-day period. The incidence rate of endometrial events will be computed on the evaluable endometrium. The 95% two-sided CI will be computed on the observed frequency of hyperplasia/carcinoma of the endometrium.

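### The Endometrial Safety Analysis Set as worded admits hyperplasia found before Month 12 but not carcinoma, which would bias the randomized part's hyperplasia/carcinoma rate if that set is its denominator

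*Protocol*

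**What the plan says.** **Who is in the set.** Protocol 12.1 opens the definition with "All randomized subjects who received at least one dose of randomized study medication, had an evaluable biopsy", so by its wording it covers randomized, treated subjects. There are two ways in. The main route is that the subject "had an evaluable biopsy at Baseline and at Month 12 (defined by a Visit window as on or after Day 326"). The early-event route is "or had a diagnosis of endometrial hyperplasia prior to Month 12". Carcinoma appears in neither.

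**What is to be estimated.** Protocol 12.8: "The 95% two-sided CI will be computed on the observed frequency of hyperplasia/carcinoma of the endometrium". The same section sets a default population: "All safety parameters will be summarized using data from the Safety Analysis Set if not indicated otherwise". It bases endometrial event frequencies on evaluable biopsies, does not mention the Endometrial Safety Analysis Set, and states neither a formal test nor a threshold for the interval.

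**How carcinoma is classed and handled.** Protocol 10.4.8 ranks the diagnoses as "carcinoma > atypical complex hyperplasia > atypical simple hyperplasia > complex hyperplasia > simple hyperplasia > benign endometrium". On management it says: "If a biopsy shows disordered proliferative endometrium, hyperplasia or worse, the study drug will be discontinued, and the subject will be withdrawn from the study".

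**What the SAP does.** The SAP covers the Safety Study part only (section 1). Its section 8 lists removal of the Endometrial Safety Analysis Set as a change from the protocol and moves the endometrial analysis to the Safety Analysis Set. Section 7.7.1.12.2 adds a worst-case summary over all on-treatment visits, unscheduled ones included, with carcinoma reported as its own category. Section 1 also cites a separate Efficacy Study Part SAP, version 3.0 of 5 April 2022, which is not available here.

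**The concern.** A set built only on Month 12 biopsies would lose every woman withdrawn because of an endometrial finding. The early-event route exists to put those women back. As worded it does so for hyperplasia and omits the more serious diagnosis, although the planned rate counts the two together.

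Any rate computed on this set would therefore err in the favourable direction. The loss would affect the outcome that matters most for endometrial safety under unopposed estrogen. With about 100 non-hysterectomized women per randomized arm and heavy expected drop-out, a single case can decide whether the reported rate is zero.

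**Working it through.** **Step 1: can an early carcinoma enter the set?**

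- *Main route.* It needs an evaluable biopsy on or after Day 326. Under Protocol 10.4.8 and 10.4.10 a subject with carcinoma stops study drug and is withdrawn. Her early-termination biopsy then normally falls before Day 326, so this route is normally closed.
- *Early-event route.* It needs a diagnosis of hyperplasia. The protocol does not use that word to cover carcinoma. The 10.4.8 hierarchy puts carcinoma above every hyperplasia grade, section 10.6 lists it as a separate event of special interest, Appendix 16.3 gives it its own code (11), and SAP Table 8 gives it its own category (6). Elsewhere the protocol adds *or worse*, or writes both terms, when it means both.
- *Loose end.* Section 12.1 does not say whose diagnosis counts. A case read as hyperplasia by one pathologist and carcinoma by another might enter.

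Read literally, then, an early carcinoma normally meets neither route.

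**Step 2: the plan's own figures.** The documents give no endometrial rate or target. The nearest stated figures are the completer counts in Protocol 8.1, and both reproduce:

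- 12 months, Efficacy Study part: 600 × (1 − 0.50) = 300.
- 3 months: 300 × 0.65 + 300 × 0.80 = 195 + 240 = 435.

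**Step 3: what one omitted case does.**

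Inputs: about 100 non-hysterectomized women per arm (Protocol 8.1.1) and 50% drop-out at one year (Protocol 8.1).

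Assumptions: the overall 50% applies to non-hysterectomized women; every completer has evaluable tissue at baseline and Month 12; there is no hyperplasia; there is one carcinoma before Day 326; the rate is computed on this set. The interval is exact (Clopper-Pearson), because Protocol 12.8 names no method.

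Women with a Month 12 biopsy per arm: 100 × (1 − 0.50) = 50.

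For 0 events in n, the upper limit is 1 − 0.025^(1/n). With n = 50 this is 1 − 0.025^(0.02) = 7.11%. For 1 event, the limits are the 2.5% quantile of Beta(1, n) and the 97.5% quantile of Beta(2, n − 1).

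| Setting | As written | Carcinoma admitted |
|---|---|---|
| One arm, 50% drop-out | 0/50 = 0% (0 to 7.11%) | 1/51 = 1.96% (0.05% to 10.45%) |
| Two E4 arms pooled, 50% drop-out | 0/100 = 0% (0 to 3.62%) | 1/101 = 0.99% (0.03% to 5.39%) |
| One arm, 35% drop-out | 0/65 = 0% (0 to 5.52%) | 1/66 = 1.52% (0.04% to 8.16%) |
| One arm, 65% drop-out | 0/35 = 0% (0 to 10.00%) | 1/36 = 2.78% (0.07% to 14.53%) |

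The protocol already expects 35% drop-out among non-hysterectomized women by 3 months, so on its own assumptions that row is a best case at 12 months.

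**The case against.** The strongest reply is that no analysis is assigned to this set. Section 12.1 gives the Safety Analysis Set all safety analyses, and 12.8 repeats that default and counts events on evaluable biopsies. On that text, a treated, randomized woman with an evaluable carcinoma biopsy is counted. This stands. A reader might infer that the protocol designates the Endometrial Safety Analysis Set for the hyperplasia/carcinoma rate, but the documents do not say so. They only imply it: 12.1 lists the set among those on which analyses will be based, its name and content fit nothing else, and SAP section 8 treats using the Safety Analysis Set as a departure from the protocol.

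Three further points also stand:

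- The Safety Study part is untouched, because its SAP drops the set and keeps early events in view.
- The Efficacy SAP may already use, reword or drop the set. However, its cited date precedes protocol version 8.0 of 21 June 2022, which still carries the clause.
- A reader might infer that an early cancer would vanish from the report. It would not: carcinoma is a named event of special interest, entered within 24 hours (Protocol 10.6), and the DSMB monitors endometrial safety (Protocol 10.5). Carcinoma found at the planned biopsy on or after Day 326 enters by the main route, given an evaluable baseline biopsy.

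The wording gap survives all of this. A defined set that admits the lesser diagnosis and omits the greater one is wrong however often it is used.

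**Conclusion.** The point holds in conditional form. The clause in Protocol 12.1 omits carcinoma, and withdrawal normally closes the other way in. If the set is used for the combined rate in the randomized Efficacy Study part, an early carcinoma leaves both numerator and denominator. On the assumptions listed, one such case moves a single arm from 1.96% (upper limit 10.45%) to 0% (upper limit 7.11%), and the two pooled E4 arms from 0.99% (5.39%) to 0% (3.62%).

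The severity is moderate. It would be tempting to treat this as a defect that must be corrected before the trial can be interpreted. The documents do not support that: the use of the set is implied rather than stated, the only SAP available discards it, no threshold hangs on the interval, and early carcinoma would still be reported as an event of special interest. The figures illustrate one hypothetical case and do not predict how many will occur.

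**What to change.** 1. In the early-event clause of Protocol 12.1, insert *or carcinoma* after *endometrial hyperplasia*. Do not restrict the clause to on-treatment diagnoses. Protocol 10.1.5.7 recognises that dosing may already have stopped by the early-termination visit, so that restriction could exclude events the clause now admits.
2. In Protocol 12.8, name the analysis set that supplies the denominator for the hyperplasia/carcinoma rate. This is the more consequential gap, since the present text leaves the reader to choose between the default set and the purpose-built one.
3. Check the Efficacy Study Part SAP and align it with both changes.

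The cost is a few words in each document, with no new data or procedures. The change should be made before anyone sees unblinded endometrial results, because a later one would look data-driven.

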8. SUBJECT SELECTION AND DISCONTINUATION/WITHDRAWAL OF SUBJECTS

8.1. Source and Number

This will be a multicenter trial performed in multiple study sites in the United States of America and Canada. Subjects will be recruited by the investigator from his/her patients or will be recruited by recruitment campaigns. Subjects must seek treatment for the relief of menopausal symptoms, or subject may already be treated for menopausal symptoms and willing to discontinue their current treatment.

All investigators must keep a record of subjects who were considered for enrollment and were consented, but were never enrolled e.g., subject screening log to address concerns over selection bias.

This trial will enroll a total of approximately 1,000 subjects; ~600 subjects ~200 per treatment arm) in the Efficacy Study part and ~400 subjects in the Safety Study part of the trial. Enrollment will stop when the minimum required number of subjects in each study group and study part is enrolled.

The number of completers after three months of treatment in the Efficacy Study part is anticipated to be around 435, anticipating a drop-out rate of 35% and 20% for non-hysterectomized and hysterectomized women, respectively. The number of completers after 12 months of treatment is anticipated to be ~300, anticipating a drop-out rate of 50% after one year of treatment.

The number of completers in Safety Study part after 12 months of treatment is expected to be ~200, anticipating a drop-out rate of 50%.

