9.3.2. Placebo (Visually Matching the Active Treatments)

Active substance No active substance

Dosage form: Film coated tablet

Excipients: █████ (co-processed excipient containing lactose monohydrate and maize starch)

Magnesium stearate

██████████ (containing hypromellose, hydroxypropylcellulose, stearic acid, talc, titanium dioxide, Brilliant Blue, Indigo Carmine and Tartrazine)

Manufacturer: ██████████

Blinding primary packaging: Blister pack (PVC/Aluminum) containing 28 tablets per blister

Supplier/secondary packaging: Carton Wallet

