9.7. Treatment Compliance

Subjects will be asked to bring all packages of used and unused trial medication, including empty blisters/bottles and wallets to each visit. Treatment compliance will be assessed by counting the returned trial medication at each visit. The counts of the returned trial medication will be recorded by the clinical staff in the subject drug accountability log. Any discrepancies between actual and expected amount of returned trial medication must be recorded and discussed with the subject at the time of the visit.

Additionally, for some subjects (see Section 10.1.7), intake of the trial medication will be recorded in a paper diary to check on treatment compliance. The diaries will be checked at each visit for any discrepancies in medication intake.

To confirm treatment compliance in the Efficacy Study part, blood samples for the analysis of E4 concentrations will be taken during Visits 2, 3 and 4.

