10.1.5.4. Visit 4: End of Primary Efficacy Period (week 13)

Subjects will return to the trial site in week 13 for Visit 4. This will be the end of the primary efficacy period. The following observations/procedures are to be performed and checked at Visit 4:

- Vital signs
- TVUS (for non-hysterectomized women only)
- MENQOL and CGI questionnaires
- Fasted blood sampling for:
 - Lipid metabolism
 - Glucose metabolism
 - Hemostasis parameters
 - Bone markers
 - E2 and E4 (fasting not required)
- Review of diary and collect completed pages
- Dispense trial medication
- Review returned unused medication/drug accountability
- Record prior/concomitant medication
- Record AEs

After completion of the Visit 4 procedures, trial medication for weeks 17 to 32 will be dispensed (see Section 9.4) and the next visit will be scheduled. Subjects are instructed to come to the next visit and take all packages of used and unused trial medication, including empty blisters and wallets. Non-hysterectomized subjects are instructed to continue daily recording of study drug intake and vaginal bleeding events in the diary and to take the diary to the next visit. Hysterectomized subjects will return their diary.

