10.3.5. Endocrine Assessment for Inclusion And Monitoring of Treatment Compliance

During screening a blood sample will be taken for assessment of FSH and E2 to confirm postmenopausal status and for the assessment of TSH to exclude inadequately treated hyperthyroidism. If TSH is outside the normal ranges, a reflex T4 will be done.

During the first 12 weeks of treatment with trial medication in the Efficacy Study part blood samples for E2 will be taken at each visit to continue monitoring the E2 levels and assess compliance with study requirements in terms of unauthorized concomitant therapies.

During the first 12 weeks of treatment with trial medication in the Efficacy Study part blood samples for E4 analysis will be taken at each visit (except at Visit 1) to confirm treatment compliance. E4 analyses will only be performed at the end of the study to avoid unblinding.

Methods for blood sample collection, processing, and shipment of these samples are described in instructional materials provided to investigational sites. Leftover samples will be retained after this trial for additional analyses in the context of this program or any further research on E4; details of the sample retention for future research as well as subject's rights in regard to these samples are presented in the ICF.

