12.5. Analysis of Primary Efficacy Variables

All statistical tests will be supported by presenting estimates and 95% CIs for the respective treatment effects (difference to placebo). These estimates and CIs will be based on the respective statistical models used for the analysis. Since all analyses of the efficacy variables are not exploratory in nature, adjustment for multiplicity will be performed (Dunnet adjustment for the comparison of each active dose versus placebo).

The primary efficacy comparison will test the following hypotheses for each treatment arm:

- H0: The average change from baseline in the primary efficacy endpoint in the treatment arm is greater (less pronounced) or equal to the average change from baseline in the placebo arm
- H1: The average change from baseline in the primary efficacy endpoint in the treatment arm is lower (more pronounced) to the average change from baseline in the placebo arm

The two dose groups of E4 will be compared to placebo regarding the four co-primary endpoints.

A comparison between treatment arms of the change from baseline at week 1 to week 12 in the weekly frequency of moderate to severe VMS and of the change from baseline in the weekly mean severity of moderate to severe VMS will be made by using Mixed-effect Models for Repeated Measures (MMRM). The MMRM models will include treatment, week, treatment by week interaction and pooled trial centers as fixed effects and baseline as a covariate. If the pooled center effect included in the model is significant, a treatment by center interaction will be included in the model. Treatment effects will be assessed at week 4 and 12 using two separate MMRM models (one on weekly frequency and another on weekly mean severity).

The primary analysis will use the data from the ITT population. Since an MMRM model is used, missing data imputation is not necessary. Additional sensitivity analyses will be implemented in order to assess the robustness of the results. These may include sensitivity with respect to:

- An imputation of missing data (last observation carried forward [LOCF] or other)
- The modelling strategy [analysis of covariance (ANCOVA) instead of MMRM]
- Confounders (for example ethnicity, hysterectomized status)
- Populations studied (mITT, PP)
- Any combination of the above

In addition, all primary efficacy variables will be tabulated at baseline and at each post-baseline time point.

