12.7. Analysis of Secondary Efficacy Variables

All VMS related secondary efficacy variables will be analyzed using the same methodology as for the primary efficacy variables and will be based on the data from the ITT population.

All other secondary continuous efficacy variables will be analyzed using either an ANCOVA or an MMRM model depending on the type of endpoint considered. These models will be evaluated using data from the ITT, PP and mITT populations without imputation of data. Appropriate covariates may be included in the analyses.

The other categorical efficacy variables (scores, responder analysis) will be analyzed using appropriate statistical methods for the comparison of each treatment arm to the placebo arm.

In addition, all secondary efficacy variables will be tabulated at baseline and at each post-baseline time point.

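### The protocol's mITT rule on E4 below the quantification limit names no arm; applied as written to assayed placebo samples, it removes nearly all placebo subjects with Week 12 data from supportive models that 12.7 commits to

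*Protocol*

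**What the plan says.** **The set.** Protocol Section 12.1 starts the mITT Set from all randomized subjects in the ITT Set. It removes anyone with "At least one post baseline E4 concentration level below the lower limit of quantification", and anyone with a post-screening E2 level above 40 pg/mL. The Synopsis (Statistical populations) gives the same two criteria. Neither place names a treatment arm.

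**The sampling.** For the Efficacy Study part, Section 9.7 says "blood samples for the analysis of E4 concentrations will be taken during Visits 2, 3 and 4". Section 10.3.5 says "blood samples for E4 analysis will be taken at each visit (except at Visit 1) to confirm treatment compliance", and defers the assay to the end of the study to avoid unblinding. Section 10.1.5.4 puts an E4 sample at Visit 4, alongside the Week 12 lipid, glucose, hemostasis and bone samples and the MENQOL. None of these sections exempts placebo.

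**The placebo.** Section 9.3.2 lists "No active substance". Section 5.1 states that humans produce E4 only in pregnancy.

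**The use of the set.** For the continuous secondary efficacy variables other than VMS, Section 12.7 and the Synopsis say "These models will be evaluated using data from the ITT, PP and mITT populations without imputation of data". For the co-primary endpoints, the mITT appears in Section 12.5 only in a list introduced by "These may include sensitivity with respect to". The supplied SAP covers the Safety Study part. It drops the mITT and describes it, in its Section 8, as meant for a sensitivity analysis of the primary efficacy endpoint.

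**The concern.** A single E4 result below the limit is enough for exclusion, and a placebo subject is expected to give one every time she is sampled. The Week 12 secondary assessments share Visit 4 with an E4 sample, so the visit that produces a placebo subject's Week 12 value would normally also exclude her. Subjects reaching Week 52 have passed all three E4 visits.

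Secondary objectives 3 and 4 in Section 6.1.2 are comparisons with placebo. An mITT model for those endpoints with almost no control subjects cannot serve them. The practical risk is that the set has to be redefined after the E4 results are known, and those results separate the arms.

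**Working it through.** **Step 1. Reproduce the plan's completer figure.** Inputs: about 300 non-hysterectomized and 300 hysterectomized subjects in the Efficacy Study part (Synopsis); dropout by 12 weeks of 35% and 20% (Section 8.1); 1:1:1 allocation (Section 7.2).

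- Completers = 300 × (1 − 0.35) + 300 × (1 − 0.20) = 195 + 240 = 435.
- Section 8.1: "The number of completers after three months of treatment in the Efficacy Study part is anticipated to be around 435". The figure reproduces.
- Per arm: 435 / 3 = 145, if the planned dropout applies equally to placebo.

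**Step 2. Apply the rule as written to placebo.** Assume placebo samples are assayed and read below the limit. A placebo completer of Week 12 then stays only if she has no E4 result from any of Visits 2, 3 and 4:

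retained = 145 × P(all three E4 results missing)

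The documents give no rate of missing samples, so the rates below are assumptions.

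| Assumption | Calculation | Placebo completers retained |
|---|---|---|
| Full sampling | 145 × 0 | 0 |
| 10% missing per sample, independent | 145 × 0.10³ | 0.15 |
| 20% missing per sample, independent | 145 × 0.20³ | 1.2 |
| 1% of subjects miss all three | 145 × 0.01 | 1.5 |
| 2% of subjects miss all three | 145 × 0.02 | 2.9 |
| 5% of subjects miss all three | 145 × 0.05 | 7.3 |

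The last three rows matter because missed samples tend to cluster within a subject. The E2 criterion could only lower these counts.

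The other placebo subjects who could stay are those among the 200 − 145 = 55 planned dropouts who left without an E4 sample. They have no Week 12 value.

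**Step 3. Week 52.** Section 8.1 expects about 300 completers at 12 months, or 300 / 3 = 100 per arm if dropout is equal. All have passed Visits 2 to 4, so the same exclusion applies.

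**Step 4. What is left of the comparison.** Detectable difference in SD units at 80% power, two-sided 5%, no Dunnett adjustment: (1.960 + 0.842) × √(1/n₁ + 1/n₂).

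- 145 against 145: 0.33 SD.
- 145 against 7: 1.08 SD.
- 145 against 3: 1.63 SD.
- 145 against 1: 2.81 SD.
- 145 against 0: the contrast cannot be estimated.

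These hold the active arm at 145, before its own E4 and E2 exclusions.

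**Step 5. With the criterion limited to the E4 arms.** Placebo retention depends only on E2 above 40 pg/mL. Assumed exclusion of 0%, 2%, 5% or 10% leaves 145, 142.1, 137.8 or 130.5 of 145.

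**The case against.** **The purpose is clear from context.** E4 is sampled to confirm compliance, and a result below the limit says nothing about compliance in a placebo subject. Deferring the assay to protect the blind shows the authors knew that E4 results separate the arms. This stands as evidence of intent: a rule for the active arms is very probably what was meant. It does not cure the text, because an analysis set should be programmable as written and no supplied section states the restriction.

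**Placebo samples may never be assayed.** No section says that they will be. If only active-arm samples are assayed, no placebo subject has an E4 level and the rule removes none. This stands, and the finding is conditional on it.

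**The Efficacy Study Part SAP may already settle it.** The supplied SAP cites that document as version 3.0 of 05Apr2022, and it is not available here. This also stands. Protocol version 8.0, dated June 21, 2022, is later and still carries the unrestricted wording, so if that SAP restricts the rule, the protocol needs aligning with it.

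**The effect is small.** Agreed. ITT is the primary efficacy population, the VMS secondary endpoints use ITT, and the affected endpoints are also modelled on ITT and PP. A near-empty placebo column would show as soon as the tables were run, and no data would be lost.

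**Conclusion.** The wording defect is real and should be fixed. Followed as written, with placebo samples assayed and below the limit, the rule leaves about 0 to 7 of some 145 planned placebo completers of Week 12 over the range of missing-sample assumptions shown. The mITT models for hemostasis, lipid, glucose, bone turnover and MENQOL changes would then have no usable control group.

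Three stronger readings are tempting, and the documents do not support them:

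- A reader might infer that the trial's efficacy conclusion is at risk. The co-primary analysis is on ITT, and its mITT version is only optional.
- A reader might infer that the mITT placebo group is empty. Subjects who leave before Visit 2 without an E4 sample stay in the set, and a few completers could stay if their missed samples cluster.
- A reader might infer that the sponsor's analysis will in fact lose its placebo arm. That depends on whether placebo samples are assayed and on the Efficacy Study Part SAP, and neither can be checked here.

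Confidence is high that the protocol names no arm. The retained counts rest on the stated assumptions: placebo assayed and below the limit, planned dropout equal across arms, and the assumed missing-sample rates.

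**What to change.** In Section 12.1 and in the Synopsis, state that the criterion on E4 below the quantification limit applies only to subjects randomized to E4 15 mg or E4 20 mg. Keep the E2 criterion for all arms. Check that the Efficacy Study Part SAP says the same, and align it if not. Do this before E4 results are available, so that the set is not redefined with knowledge of them.

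The cost is one phrase in each of two places and a check of one document. No new data are needed, and sampling and assay timing do not change. There is a small downside: the E4 filter then selects on compliance in the active arms only, so the mITT contrast is no longer a like-for-like randomized comparison and should stay supportive to the ITT result.
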